7.1. Primary Efficacy Endpoint Analysis

The primary efficacy endpoint is defined as:

- Comparison in the percentage of patients on SEL-212 vs. KRYSTEXXA® who achieve and maintain reduction of SUA < 6 mg/dL for at least 80% of the time during Treatment Period 3 and Treatment Period 6

The SUA time curve will be used to estimate the proportion of time that the SUA level is below 6 mg/dL. Based on the serum samples collected during Treatment Periods 3 and 6, an estimate of the time with SUA < 6 mg/dL can be determined by connecting each two neighboring data points with a straight line. SUA values collected at unscheduled visits within period 3 and period 6 will be included for the SUA time curve. If the SUA time curve goes above 6 mg/dL the linear interpolation method will be used to estimate the point in time at which the SUA time curve intercepts the line between the last SUA value < 6 mg/dL and the first value \geq 6 mg/dL.

The proportion of time that the SUA level is < 6 mg/dL will be computed by taking the ratio between the time during which the SUA level remains < 6 mg/dL (if necessary, using the linear interpolation method) and the entire time interval within Treatment Periods 3 and 6. For period 3, entire time interval is between time of day 0 SUV assessment for period 3 and period 4. For Period 6, the entire time interval is between time of day 0 and day 28 assessment.

Let T1 be the total time interval in hours for Treatment Period 3 of which W1 hours is the time interval during which SUA level is < 6 mg/dL. Similarly, for Treatment Period 6, assume T2 is the total time interval in hours of which W2 hours is the time interval during which SUA level is < 6 mg/dL. For a patient to be considered a responder, the proportion of time that the SUA level is < 6 mg/dL during Treatment Periods 3 and 6 must be at least 80%. The proportion of time that the SUA level is < 6 mg/dL, i.e., percentage (p) of non-hyperuricemic time, is calculated using the following formula:

$$\text{Percentage (p)} = \frac{W1 + W2}{T1 + T2} \times 100$$

Missing scheduled assessments of SUA will be imputed as follows: If SUA is missing at day 0 (predose) for periods 3, 4 and 6 and day 28 for period 6 in the SEL-212 cohort, baseline SUA will be used for calculation. If SUA is missing at day 0 (predose) for periods 3, 4 and 6 and day 28 for period 6 or day 14 (pre-dose) for treatment periods 3 and 6 in the Krystexxa cohort, baseline SUA will be used for calculation. Day 0 predose time point is the same as day 28 of previous treatment period. For example, period 4 predose is same as period 3 day 28. If SUA is missing at the post-dose timepoint on dosing days (ie post-treatment on Day 0 in SEL-212 cohort or post-treatment on either D0 or D14 in Krystexxa cohort) in either Treatment period 3 or 6 or is missing at Day 21 of treatment period 3 or 6 for the SEL-212 cohort for a patient, it will be imputed by the mean of the available assessments at the respective time from the prior Treatment Periods (ie from Treatment periods 1 and 2 for missing data in TP3 and from Treatment periods 1 to 5 for missing data in TP6) of this patient. Missing SUA assessments at Day 7 and Day 14 in the SEL-212 cohort and missing SUA assessments at Day 7 and 21 in the Krystexxa cohort will not be imputed, but SUA time curve will be determined by interpolation.

This document is confidential.

If the duration of the Treatment Period 3 or 6 has been extended by more than 6 days beyond its nominal 28 day duration due to study visits occurring beyond their protocol windows, the corresponding TP4 day 0 (predose) or TP6 day 28 value will be imputed by the baseline value for the patient at the timepoint of 28 days after the previous Day 0 timepoint (TP3 or TP6) and only those SUA values drawn within 28 days of the respective day 0 (ie. TP3 or TP6) will be used in calculating the proportion of time that the SUA level is below 6 mg/dL.

The primary estimand will take into consideration the treatment policy strategy, ie, Treatment Period 3 and 6 assessments will be considered for all patients in ITT independently whether the patient has completed the study treatment or has terminated the study treatment early. If a subject withdraws from study before completing period 6 or is put back on ULTs, the subject will be considered as a non-responder for the primary efficacy endpoint. The return of ULTs is a confounding factor for subsequent SUA efficacy.

The estimator for the comparison between the treatment groups is defined as the difference in the proportion of responders between patients receiving SEL-212 versus those receiving KRYSTEXXA® during Treatment Periods 3 and 6. The statistical testing will be performed confirmatory using the Cochran-Mantel-Haenszel (CMH) test – considering the randomization stratum of tophus presence (yes/no) – with a one-sided type 1 error rate $\alpha = 5\%$. In addition, 90% two-sided confidence intervals for the overall treatment difference between SEL-212 and KRYSTEXXA® treatment groups without stratification will be computed. The analysis of the estimands will be carried out based on the ITT primarily. Supportive analyses will be performed on the mITT and the PP.

A logistic regression model to compare treatment difference controlling for presence of tophus will be performed as supportive analysis.

In addition, a sensitivity analysis will be performed as below for the primary endpoint:

- If a subject withdraws from study treatment before completing period 6 due to stopping rules met for treatment, the subject will be considered as a non-responder for the primary efficacy endpoint.
- If a subject withdraws from the study before completing period 6 or the study terminates prior to a subject completing period 6, the primary efficacy endpoint is based on SUA assessment for period 3 where $T1$ be the total time interval in hours for Treatment Period 3 of which $W1$ hours is the time interval during which SUA level is < 6 mg/dL:

$$\text{Percentage (p)} = \frac{W1}{T1} \times 100$$

Summary tables of the percentage of responders (patients who achieve and maintain reduction of SUA < 6 mg/dL for at least 80% of the time) will be provided by treatment group. Additionally, a summary table with the total time a patient has SUA values < 6 mg/dL will be provided for treatment period 3 and treatment period 6 by treatment group.

Summary tables of the actual values and change from baseline for SUA results will be provided for each scheduled sampling time point by treatment group.

This document is confidential.

Additionally, mean SUA level, reduction in mean SUA and percent reduction in mean SUA from baseline during Treatment Periods 3 and 6, during Treatment 3, and during Treatment Period 6 will be summarized by treatment group respectively and will be compared for treatment difference using ANOVA model with presence of tophus and treatment group as fixed factors

- Mean SUA level is defined as the area under the SUA time curve (computed using the linear trapezoidal rule during Treatment Periods 3 and 6) divided by the corresponding time interval.
- Reduction in mean SUA is computed by subtracting baseline SUA level from mean SUA during Treatment Period 3 and 6.
- Percent reduction in the mean SUA from baseline is computed as the mean SUA level during Treatment Periods 3 and 6 minus baseline SUA level divided by baseline SUA level multiplied by 100

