7. INVESTIGATIONAL PLAN

7.1 Overall Study Design

This study is a randomized, open-label, parallel-arm study to compare the safety and efficacy profiles of SEL-212 and KRYSTEXXA. Approximately 150 patients will be randomized 1:1 prior to Baseline to receive treatment with SEL-212 or KRYSTEXXA for 6 months. Efficacy assessments, as measured by SUA levels, will be conducted at intervals that are appropriate to determine treatment effect differences, including at month 3 and month 6. Assessments of qualitative endpoints will be conducted on an assessor-blinded basis. Safety will be monitored throughout the study.

The study will be divided into 3 study periods: Screening, Treatment, and Follow-up, described below. The study is depicted schematically in [Figure 1](#).

The total duration of participation in the study will range from approximately 26 to 31 weeks (184 to 219 days) for patients randomized to SEL-212 and approximately 28 to 33 weeks (198 to 233 days) for patients randomized to KRYSTEXXA as follows:

- Screening and/or washout and premedication period: up to 45 days (up to 6.5 weeks)
- Treatment: 168 days (24 weeks) for SEL-212 KRYSTEXXA
- Safety Follow-Up: 30 (+ 4) days after the date of last infusion
 - SEL-212: Last scheduled infusion on Study Day 140
 - KRYSTEXXA: Last scheduled infusion on Study Day 154

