Appendix A SCHEDULE OF ASSESSMENTS FOR PATIENTS RANDOMIZED TO SEL-212, CONTINUED

Assessment	Scr.	Treatment Period (TP)																EOS ¹	ET			
		TP1 ²		TP2 ²		TP3 ²				TP4 ²		TP5 ²		TP6 ²								
Day	-45 d	-7 d ³	D0	D21	D0 ⁴	D21	D0 ⁴	D7	D14	D21	D0 ⁴	D21	D0 ⁴	D21	D0 ⁴	D7	D14	D21	D28 ²⁰			
Health Questionnaires ¹⁸			X										X							X		X
Collect Sample for SUA	X				Refer to Schedule of Assessments in Appendix B for SUA Sample Collection during Treatment Period																	X
Study Drug Administration					Refer to Schedule of Assessments in Appendix B for Study Drug Administration during the Treatment Period																	
Concomitant Medications / Procedures					Continuously																X	X
AE/SAE Collection	X ¹⁹	X ¹⁹			Continuously																X	X

1. Phone call at 30 (+ 4) days after the last study drug infusion for assessment of concomitant medications/procedures, AEs, and SAEs.
2. Visit window at Day 21 of each Treatment Period is -2 days to +1 day.
3. Visit window is -2 days.
4. Study drug dosing to occur 28 days from the previous dose with a window of -4 days to +3 days of the intended dosing day.
5. Full physical exam
6. Directed physical exam
7. Assess vital signs on Day 0 at Time 0 (pre-dose), within + 5 minutes after completion of infusion of the first component of study drug, and 1 hour (+ 5 minutes) after completion of infusion of the second component of study drug.
8. Height measured once during Screening only.
9. Screening labs to include: SUA, anti-PEG-antibodies, hepatitis B and C antibodies, human immunodeficiency virus 1/2 (HIV1/2), hemoglobin-A1c (HbA1c), glucose, triglycerides, LDL, glucose-6-phosphate dehydrogenase (G6PD), WBC, AST, ALT, Hgb, serum creatinine, and serum phosphate, urinalysis
10. Begin ULT washout at least 7 days prior to Day 0 of Treatment Period 1.
11. Begin colchicine 0.6 mg QD premedication at least 7 days prior to Day 0 of Treatment Period 1. Patients not already taking colchicine will receive colchicine 1.2 mg as a single loading dose followed by the 0.6 mg every day regimen. If the patient cannot tolerate the loading dose level of 1.2 mg, then the patient will initiate and maintain colchicine at 0.6 mg.
12. Pretreatment to minimize potential infusion reactions: oral steroids at 24 (\pm 12) hours and oral antihistamines at 12 (\pm 2) hours and 2 (\pm 1) hours and IV steroids at 1 (\pm 0.5) hours prior to study medication.

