13. Chemistry labs to include: Alkaline phosphatase, alanine aminotransferase (ALT), aspartate aminotransferase (AST), total bilirubin, blood urea nitrogen (BUN), creatinine, fibrinogen, glucose (fasting), phosphorous, electrolytes (sodium, potassium, chloride, bi-carbonate, phosphate and magnesium).
14. Hematology labs to include: white blood cells (WBC) count with differential, red blood cell (RBC) count, hematocrit (Hct), hemoglobin (Hgb), mean corpuscular volume (MCV), mean corpuscular hemoglobin (MCH), mean corpuscular hemoglobin concentration (MCHC), red cell distribution width (RDW), platelet (Plt) count, mean platelet volume (MPV)
15. Coagulation labs to include: prothrombin time (PT), activated partial thromboplastin time (aPTT), international normalized ratio (INR)
16. Lipid labs to include: total cholesterol, HDL, LDL, triglycerides
17. Urinalysis to include: urinary protein, albumin, creatinine, pH, specific gravity, blood, glucose, ketones, bilirubin, leukocyte, esterase, WBC, RBC, crystals, casts (cast types), epithelial cells (renal and nonrenal), bacteria, mucus, and yeast.
18. Refer to [Section 11.3](#) for Health Questionnaires.
19. During Screening, SAE collection begins at time of signing informed consent. Non-serious AE will not be collected during Screening.
20. Visit window is -2 days to +6 days

Abbreviations: Ab: antibody; D (d): day; ECG: electrocardiogram; EOS: end of study; ET: early termination; h: hour; RCTC: Rheumatology Common Toxicity Criteria; Scr: Screening Period; SUA: serum uric acid; TP: treatment period; ULT: urate lowering therapy

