5.6. Protocol Deviations

All protocol deviations related to study inclusion or exclusion criteria, conduct of the trial, patient management, dosing, and sampling procedures or patient assessment will be listed. The list of protocol deviations will be reviewed by the Sponsor, the principal investigator, the study statistician and the study pharmacokineticist and finalized before database lock. Determination of whether the deviation is major or minor, or has impacts on primary efficacy assessment will be based on the biasing impact of the deviation on the safety and efficacy data. Major protocol deviations affecting the primary efficacy assessments include: 1) major protocol deviations that lead to premature study drug discontinuation; 2) major protocol deviations that lead to patients receiving study drug treatment in treatment periods 3 or 6 that they would not otherwise have received (such as incorrect application of the protocol stopping rules that allow a patient to continue dosing despite having met the stopping criteria); and 3) protocol deviations that involve out of window sampling of SUA due to a) visits occurring outside of the protocol visit window for dosing days (where dosing days refer to dosing visits of patients still on study drug who have not previously been withdrawn from study drug) in Treatment period 3 and 6, b) visits occurring outside of the protocol visit

This document is confidential.

window for visits within TP3 or TP6 scheduled 1 week prior to the dosing days, c) visits occurring outside of the protocol visit window for TP6 D21 for patients who have not been withdrawn from study drug and for dosing day TP4D0, or d) visits occurring 35 days or more beyond TP6D0 for the TP6D28 visit for patients who have not been withdrawn from study drug, where the protocol visit window above refers to the current protocol window allowed at the time of analysis. Major protocol deviations affecting the primary efficacy assessments will be reviewed and determined periodically during clinical and medical review of protocol deviations during the study.

Protocol deviations related to Covid-19 will be identified and flagged.

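### TP6 time ends at the actual Day 28 visit (Day 26 to 34 in window), so near-threshold scoring depends on visit date, mainly for the TP6-only endpoints

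*SAP*

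**What the plan says.** SAP 7.1 scores a patient as a responder when (W1 + W2)/(T1 + T2) is at least 80%. W is the time below 6 mg/dL and T the length of TP3 (subscript 1) or TP6 (subscript 2). T1 ends at the TP4 Day 0 sample. For T2 the text is: "For Period 6, the entire time interval is between time of day 0 and day 28 assessment". T2 is therefore elapsed time to a visit, not a fixed 28 days.

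For that visit, footnote 20 of Protocol Appendix A reads "Visit window is -2 days to +6 days", and Appendix C gives the same window for KRYSTEXXA. In-window T2 runs from 26 to 34 days in both arms.

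SAP 7.1 has one correction for long periods. Its condition is "If the duration of the Treatment Period 3 or 6 has been extended by more than 6 days beyond its nominal 28 day duration". Baseline SUA is then placed at 28 days, and "only those SUA values drawn within 28 days of the respective day 0" enter the calculation. The per-protocol deviation rule in SAP 5.6 starts at a similar point: "visits occurring 35 days or more beyond TP6D0 for the TP6D28 visit for patients who have not been withdrawn from study drug". Neither rule reaches Days 29 to 34, and no sensitivity analysis in SAP 7.1 or 7.4.1 does.

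On the last doses, Protocol 7.1 states "SEL-212: Last scheduled infusion on Study Day 140", which is TP6 Day 0. The last KRYSTEXXA infusion is on Study Day 154, which is TP6 Day 14. In both arms the nominal dosing interval ends at TP6 Day 28 and no dose follows. In earlier periods the next SEL-212 dose is due by Day 31: "Study drug dosing to occur 28 days from the previous dose with a window of -4 days to +3 days" (Appendix A, footnote 4).

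**The concern.** Dividing by actual elapsed time would be harmless if the extra days were like the rest of the period. They are not: they all fall at the end, after the interval the last dose was meant to cover. If SUA has risen above 6 mg/dL and stays there, each day of delay adds to T2 and nothing to W2. Two patients with the same SUA course can then be scored differently because one attended on Day 28 and the other on Day 34, both in window.

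The existing cut makes this harder to defend. A patient one day outside the window is scored on a 28-day period, while a patient on the last day of the window is scored on 34 days. The later, non-compliant visit can give the more favourable result.

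**Working it through.** The plan gives no figure for this effect. Its sample size of 69 per arm (65% vs 44%, one-sided 5%, 80% power, chi-square without continuity correction) reproduces and does not depend on T2.

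**Inputs.** Responder rule and T2 from SAP 7.1; T2 of 26, 28 or 34 days from footnote 20; truncation above 34 days from SAP 7.1. Assumption: TP3 fully controlled, W1 = T1 = 28 days.

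**1. Days below 6 mg/dL needed in TP6.** For the TP6-only 80% endpoint this is 0.8 × T2. For the primary endpoint it is 0.8 × (28 + T2) − 28.

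| Visit day | TP6-only 80% | Primary |
|---|---|---|
| 26 | 20.8 | 15.2 |
| 28 | 22.4 | 16.8 |
| 34 | 27.2 | 21.6 |

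**2. A change on the primary endpoint.** Take SUA below 6 from TP6 Day 0, 2 on Day 14, 6.5 on Day 21 and 8 at the last visit. The curve crosses 6 at 14 + 7 × (6 − 2)/(6.5 − 2) = Day 20.22, so W2 = 20.22 days whatever the date of the last visit.

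- Day 28: (28 + 20.22)/56 = 86.1%, responder.
- Day 34: 48.22/62 = 77.8%, non-responder.
- Day 35: truncation sets T2 to 28 days with baseline SUA at that point. For any baseline of at least 6 the crossing is unchanged, and 48.22/56 = 86.1%, responder.

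Status changes where 48.22/(28 + T2) = 0.8, that is at T2 = 32.3 days, inside the window.

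**3. A change on the TP6-only 80% endpoint.** Take SUA 5.0 on Day 21 rising in a straight line to 9.0 on Day 34. The crossing is at 21 + 13 × (1/4) = Day 24.25. Over 34 days this is 24.25/34 = 71.3%, a non-responder; over 28 days it is 24.25/28 = 86.6%, a responder. On the primary endpoint the same patient is a responder both ways: 52.25/62 = 84.3% and 52.25/56 = 93.3%.

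**4. A change on the TP6 100% endpoint.** Take SUA 1.0 on Day 21 and 8.0 on Day 34. The crossing is at 21 + 13 × (5/7) = Day 30.3, so the patient fails. Interpolated SUA on Day 28 is 1 + 7 × (7/13) = 4.8, so the patient is below 6 through Day 28.

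**The case against.** The strongest reply concerns size. Days after Day 28 cannot by themselves cost a fully controlled patient the primary endpoint. With SUA below 6 throughout TP3 and to TP6 Day 28, then above 6 for all of Days 28 to 34, the score is 56/62 = 90.3%. A change on the primary needs loss of control within the dosing interval. If Day 21 is still below 6, the crossing must fall between Days 21 and 21.6; with 9.0 on Day 34, the Day 21 value must lie between about 5.86 and 6.0. All of this stands.

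Few patients may be exposed. The stopping rules in Protocol 7.4.1 take many patients with high SUA off drug before TP6; if their SUA then stays above 6, W2 is near zero on any visit date. Protocol 7.6.3.2 reports that all evaluable Part C patients below 6 at Week 12 were also below 6 at Week 24. This makes a small number plausible but does not give one. The more exposed endpoints are secondary, and SAP 7.2 gives them no hierarchy.

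If the last value is the same whatever the visit date, and Day 21 is below 6, interpolation moves the crossing later and partly offsets the effect. With 4.5 on Day 21 and 8 at the last visit, the TP6-only score still falls from 85.7% (Day 28) to 78.2% (Day 34).

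Actual elapsed time is also a prespecified choice. That is true, but the SAP itself treats 28 days as nominal and cuts there once a visit is late enough.

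A reader might infer that the open-label design turns this into bias for one arm. The documents do not support that: the window is identical in both arms, no stopping rule depends on the TP6 Day 28 value, and nothing indicates that visit dates would differ by arm.

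**Conclusion.** The point holds as a scoring weakness. In-window visits on Days 29 to 34 count up to 6 undosed days, and responder status can go from yes to no and back to yes as the visit moves from Day 28 to 34 to 35. The main effect is on the TP6-only endpoints: the 80% threshold moves by 6.4 days across the window (20.8 to 27.2), and the 100% endpoint can fail on a rise after Day 28. On the primary endpoint only near-threshold patients are affected; with TP3 at 28/28 days these are the patients who lose control at about TP6 Day 15.2 to 21.6.

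This is classification error of unknown direction. The documents do not give the number of patients affected, so neither a shift in the treatment difference nor a loss of power can be claimed. The results rest on the SAP's linear interpolation, on TP3 being fully controlled, and, for the Day 35 result, on a baseline of at least 6 mg/dL.

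Nor does it follow that T1 should be cut at 28 days as well. TP3 ends at the TP4 Day 0 sample, and any days beyond 28 come before the next scheduled dose and belong to that period.

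**What to change.** In SAP 7.1, before any endpoint is calculated:

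- Cap T2 at 672 hours after the TP6 Day 0 sample. If the Day 28 sample is in window but later than 672 hours, use it only to interpolate SUA at 672 hours. If it is earlier, T2 ends at that sample, as now.
- Apply the same cap to the TP6-only responder endpoints and to the mean-SUA endpoints for TP6.
- Leave T1 ending at TP4 Day 0.
- Report the uncapped calculation as a sensitivity analysis.

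This costs one SAP sentence and one programming rule. It needs no new data and changes no visit or dosing rule. With the cap, the patient in step 2 scores 86.1% at Days 28, 34 and 35.

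There are three downsides. Up to 6 days of observed time is not counted. Interpolation to 672 hours still depends partly on the late sample: with true SUA of 4.0 on Day 21, 5.5 on Day 28 and 9.0 on Day 34, a Day 34 attender has an interpolated crossing at 21 + 13 × (2/5) = Day 26.2 and fails the 100% endpoint, whereas a Day 28 attender passes. That is no worse than the current rule, under which the Day 34 attender also fails. Finally, the Day 26 to 28 variation remains, so the in-window spread of T2 falls from 8 days to 2, not to zero.

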13.4 Efficacy Analyses

13.4.1 Primary Efficacy Endpoint

The primary efficacy endpoint is defined as:

- Comparison in the percentage of patients on SEL-212 vs. KRYSTEXXA who achieve and maintain reduction of SUA < 6 mg/dL for at least 80% of the time during Treatment Period 3 and Treatment Period 6

The primary estimand will take into consideration the treatment policy strategy, ie, Treatment Period 6 (and also Treatment Period 3) assessments will be considered for all subjects in ITT independently whether the subject has completed the study treatment or has terminated early the study treatment. Additionally, the estimand based on the while-on-treatment strategy for dealing with study treatment terminators will be defined. For all used estimands of the primary efficacy, the estimator for the comparison between the treatment groups is defined as the difference in the proportion of responders between subjects receiving SEL-212 versus those receiving KRYSTEXXA during Treatment Periods 3 and 6. The statistical testing will be performed confirmatory using the Cochran-Mantel-Haenszel (CMH) test – considering the randomization

stratum of tophus presence (yes/no) – with a one-sided type 1 error rate $\alpha = 5\%$. In addition, 90% two-sided confidence intervals for the overall treatment difference between SEL-212 and KRYSTEXXA treatment groups without stratification will be computed. The analysis of the estimands will be carried out based on the ITT primarily. Supportive analyses will be performed on the mITT and the PP. For each defined estimand sensitivity analyses will be performed using different imputation approaches for missing values. Details of the applied approaches will be presented in the Statistical Analysis Plan.

The SUA time curve will be used to estimate the proportion of time that the SUA level is below 6 mg/dL. Based on the serum samples collected during Treatment Periods 3 and 6, an estimate of the time with SUA < 6 mg/dL can be determined by connecting each two neighboring data points with a straight line. If the SUA time curve goes above 6 mg/dL the linear interpolation method will be used to estimate the point in time at which the SUA time curve intercepts the line between the last SUA value < 6 mg/dL and the first value ≥ 6 mg/dL.

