5.8. Key Definitions

Baseline is defined as the last non-missing value prior to the start of infusion of SEL-212 or KRYSTEXXA®.

Day 0 of Treatment Period 1 is defined as the first date of study drug administration.

Study day within each treatment period will be calculated as date of event/collection – first dose date at each treatment period to be consistent with protocol defined day 0.

Overall study day will be calculated as date of event/collection – first dose date of the study.

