5.9. Missing Data

Missing data will not be imputed unless specified otherwise. Missing eCRF data due to Covid-19 will be listed.

This document is confidential.

6. Demographic, Other Baseline Characteristics and Medication

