7.2.1. Secondary Efficacy Endpoints based on SUA

For the following secondary endpoints, the comparison between SEL-212 and KRYSTEXXA® will be done similar to the primary efficacy endpoint using a CMH-test considering the randomization stratum of tophus presence (yes/no) with one-sided type 1 error rate level of $\alpha=5\%$. In addition, 90% confidence intervals for treatment differences between SEL-212 and KRYSTEXXA® treatment groups will be computed. The efficacy analyses will be carried out based on the ITT and PP Sets. mITT analyses will be performed as supportive.

- percentage of patients who achieve and maintain reduction of SUA < 6 mg/dL for at least 80% of the time during Treatment Period 3
- percentage of patients who achieve and maintain reduction of SUA < 6 mg/dL for at least 80% of the time during Treatment Period 6
- percentage of patients who achieve and maintain reduction of SUA < 6 mg/dL for 100% of the time during Treatment Period 6
- percent of patients whose pre-dose SUA values > 6 mg/dL during Treatment Periods 2-6

A summary table of the number and percentage of patients who achieve and maintain reduction of SUA < 6 mg/dL for at least 80% of the time during Treatment Period 6 will be provided by treatment group.

A summary table of the number and percentage of patients who achieve and maintain reduction of SUA < 6 mg/dL for at least 80% of the time during Treatment Period 3 will be provided by treatment group.

A summary table of the number and percentage of patients who achieve and maintain reduction of SUA < 6 mg/dL for 100% of the time during Treatment Period 6 will be provided by treatment group.

A summary table of the number and percentage of patients who achieve and maintain reduction of SUA < 6 mg/dL for 100% of the time during Treatment Period 3 will be provided by treatment group.

A summary table of the number and percentage of patients with pre-dose SUA values > 6 mg/dL during Treatment Periods 2-6 will be provided by treatment group.

This document is confidential.

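### SAP 7.1 fills missing mid-period SUA differently by arm and no planned sensitivity analysis varies those fills; the Treatment Period 6 100%-of-time endpoint is where this can matter

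*SAP*

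**What the plan says.** SAP 7.1 gives these rules for a sample missing within TP3 or TP6:

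| Missing sample | SEL-212 | KRYSTEXXA |
|---|---|---|
| Day 7 | interpolated | interpolated |
| Day 14 (pre-dose for KRYSTEXXA) | interpolated | baseline |
| Day 21 | mean of own earlier Day 21 values | interpolated |

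For KRYSTEXXA Day 14 the text is "or day 14 (pre-dose) for treatment periods 3 and 6 in the Krystexxa cohort, baseline SUA will be used for calculation". For SEL-212 Day 21 the text reads: "missing at Day 21 of treatment period 3 or 6 for the SEL-212 cohort for a patient, it will be imputed by the mean"; what is averaged is that patient's own values from earlier periods. "Missing SUA assessments at Day 7 and Day 14 in the SEL-212 cohort" are left unfilled and bridged by the curve, as are KRYSTEXXA Days 7 and 21.

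A patient who leaves the study before completing TP6, or goes back on urate-lowering therapy (ULT), is handled in the same section: "the subject will be considered as a non-responder for the primary efficacy endpoint".

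On scope, SAP 5.9 says "Missing data will not be imputed unless specified otherwise". SAP 7.2.1 says the comparison for the secondary SUA endpoints "will be done similar to the primary efficacy endpoint using a CMH-test considering the randomization stratum of tophus presence", which names the test and is silent on fills and on the non-responder rule.

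Protocol 13.4.1 undertakes, for the primary endpoint: "For each defined estimand sensitivity analyses will be performed using different imputation approaches for missing values", with details left to the SAP.

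**The concern.** The two arms' fills pull in different directions. The KRYSTEXXA Day 14 fill is a pre-treatment value, normally high. The SEL-212 Day 21 fill is an on-treatment value and is low for any patient still being dosed. Where the endpoint tolerates no time at or above 6 mg/dL, the first fill decides the result and the second leaves it untouched. A missing sample then lowers the responder rate in one arm only, and that favors SEL-212.

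Nothing planned would show this. The SAP 7.1 sensitivity analysis varies how withdrawals are scored, and the SAP 7.4.1 laboratory analysis varies the laboratory source. Neither changes a mid-period fill, and SAP 7.4 does not list the protocol's commitment as dropped.

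Separately, the non-responder rule names only the primary endpoint. Protocol 7.4.1 lets a withdrawn patient return to ULT 60 days after the last dose while visits continue to the end of TP6. As written, such a patient could count as a responder on the TP6 endpoints.

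**Working it through.** **Inputs from the documents.** Planned rates 65% and 44%, one-sided 5%, 80% power, 69 per arm, 75 randomized per arm (Protocol 13.1); threshold 6 mg/dL with linear interpolation (SAP 7.1); post-dose sample about 3 h after the start of a KRYSTEXXA infusion, i.e. 0.125 day (SAP Table D). "Baseline is defined as the last non-missing value prior to the start of infusion" (SAP 5.8), so the Screening criterion of at least 7 mg/dL does not set a minimum for baseline.

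**Assumptions.** All other samples 0.5 mg/dL, infusions given, baseline B of 7 to 10, missing rates of 2, 5 and 10%. The documents give none of these.

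**Plan's own figure.** The two-proportion formula with pooled variance and no continuity correction returns 69 per arm; power is 80.3% at 69 and 83.1% at 75.

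**1. One missing KRYSTEXXA Day 14, filled with baseline.** The curve rises over 7 days and falls over 0.125 day, so time at or above 6 is 7.125 × (B − 6)/(B − 0.5) days.

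| B | Days at or above 6 | Period % below 6 | Pooled TP3 + TP6 % |
|---|---|---|---|
| 7 | 1.10 | 96.1 | 98.0 |
| 8 | 1.90 | 93.2 | 96.6 |
| 9 | 2.51 | 91.0 | 95.5 |
| 10 | 3.00 | 89.3 | 94.6 |

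The pooled column takes the other period as 100%. Every row fails TP6 100% and passes the pooled 80% rule. A baseline of 5.5 would pass both. In a harder case (B = 12, other values 5) the period figure is 1 − 7.125 × (6/7)/28 = 78.2%, and pooled it is still 89.1%.

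**2. One missing SEL-212 mid-period sample.** Days 7 and 14 are bridged between values below 6. For Day 21, the stopping rule (Protocol 7.4.1.1) caps the fill for a patient still on drug with all earlier values available: (1 + 6)/2 = 3.5 in TP3 and (1 + 4 × 6)/5 = 5.0 in TP6. The patient stays at 100%.

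**3. Effect on the TP6 100% test.** Let both arms have true rate p, and let a fraction r of KRYSTEXXA responders miss Day 14 with baseline above 6. The KRYSTEXXA rate becomes p(1 − r). The rejection probability is Φ[(Δ − 1.645·SE0)/SE1], with Δ = pr, SE0 pooled and SE1 unpooled, n = 75 (an unstratified approximation to the CMH test). For p = 0.44 and r = 0.05: Δ = 0.022, SE0 = SE1 = 0.0808, argument −1.373, rejection 8.5%.

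| p | r = 2% | 5% | 10% |
|---|---|---|---|
| 30% | 5.9% | 7.4% | 10.8% |
| 44% | 6.2% | 8.5% | 13.6% |
| 65% | 7.0% | 10.9% | 20.4% |

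At 44% the false gap is 0.9, 2.2 or 4.4 points.

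**4. TP6 at least 80%.** Take a late loss of control with Day 21 missing.
- SEL-212, Days 14/21/28 = 2/8/9. Observed: (14 + 7 × 4/6)/28 = 66.7%. Filled with 0.5: (21 + 7 × 5.5/8.5)/28 = 91.2%.
- KRYSTEXXA, Day 14 post-dose 0.5, Days 21/28 = 8/9. Observed: (14.125 + 6.875 × 5.5/7.5)/28 = 68.5%. Interpolated: (14.125 + 13.875 × 5.5/8.5)/28 = 82.5%.

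Both rules can create a false responder, so the net arm effect is not determined. A borderline SEL-212 patient (Days 14/21/28 = 5/8/9, TP3 at 100%) can also change pooled status: 79.2% observed, 95.6% filled.

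**5. Mean SUA.** One baseline fill raises a KRYSTEXXA patient's period mean from 0.5 to 1.33–1.71 (B = 7 to 10). Averaged over an arm with 2–10% missing, that is 0.02–0.12 mg/dL.

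**The case against.** **The split follows the calendar.** Pre-dose troughs take baseline in both arms, and Day 14 is a trough only for KRYSTEXXA. Day 21 is sampled in every period only for SEL-212. This largely stands and is why the rules should stay as the main analysis. It does not explain why a KRYSTEXXA Day 14 trough takes baseline when the patient's own earlier Day 14 pre-dose values exist.

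**The secondary endpoints carry no protected claim.** SAP 7.2 gives them no hierarchy, and the confirmatory label is used only for the primary test. The protocol's commitment on imputation also concerns the primary. Both points stand and limit the weight of the rejection rates.

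**The size rests on assumed missingness.** The pre-dose sample is required at each infusion and the KRYSTEXXA stopping rule depends on it, so few may be missing. At 44%, 5% missing is 0.05 × 33 = 1.65 patients of 75. This stands.

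**Stronger readings the documents do not support.**
- A reader might infer from SAP 5.9 that no fill reaches the secondary endpoints, so that the same patient scores 100%. But the SAP 7.1 fill paragraph opens in general terms, the single-period endpoints use the same curve, and mean SUA is defined within 7.1. Carry-over is the better reading; it only needs saying.
- A reader might infer that a post-dose value is filled where no infusion was given. SAP 7.1 ties that fill to post-treatment samples, which largely answers the point.
- A reader might infer that the primary result is biased toward SEL-212. Step 1 does not bear that out.

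**Conclusion.** The point holds for the single-period SUA endpoints and most clearly for TP6 100%. There, one missing KRYSTEXXA Day 14 with baseline above 6 is an automatic failure that has no SEL-212 counterpart. The one-sided 5% test then runs at 6.2 to 13.6% for an equal true rate of 44% and 2 to 10% missing at random. Those rates, the baselines and the on-drug SUA values are assumptions; with nothing missing there is no effect.

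The pooled primary is little affected: one missing KRYSTEXXA Day 14 leaves 94.6–98.0% at baseline 7 to 10, although a borderline patient can change status. The arm-level shift in mean SUA is small.

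Two gaps do not depend on any missing rate. The protocol's promised imputation sensitivity analyses do not appear in the SAP for these fills, and the non-responder rule is worded only for the primary. Both should be fixed before analysis. Neither undermines the trial's main comparison.

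**What to change.** Keep the SAP 7.1 fills as the main rule. Interpolating everywhere is not a safe replacement: with Day 7 at 0.5, 3 or 5 and a true KRYSTEXXA Day 14 trough of 7, 8 or 9, interpolation scores all nine cases as 100%, against 81–96% if observed.

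1. In SAP 7.1, pre-specify a sensitivity analysis that sets every missing Day 7, Day 14 (pre-dose for KRYSTEXXA) and Day 21 SUA in TP3 and TP6 to baseline in both arms. Run it for the primary, TP3 at least 80%, TP6 at least 80%, TP6 100% and mean SUA. Report it beside the main result as a stress test and say where the conclusion depends on the fill. Do not make claims conditional on it.
2. In SAP 7.2.1, state that the 7.1 fills apply to the TP3 and TP6 SUA endpoints. State also that a patient who leaves the study or returns to ULT before the scored period ends is a non-responder for that period.
3. Report missing TP3 and TP6 samples by arm and time point.

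**Cost.** A few sentences and one extra run; the SEL-212 advantage on secondary SUA endpoints may look slightly smaller. The run is harsh, which is why it should not gate claims. Each arm has three mid-period samples, so with baselines above 6 a TP6 100% rate p becomes p(1 − r)³ in both arms. Rejection under equal rates returns to 5.0%. If the true TP6 100% rates were 65% and 44% (assumed), power falls from 83.1% to 78.6/71.7/60.8% at 2/5/10% missing per sample. It is also not perfectly even on the 80% endpoints: at baseline 10, one missing SEL-212 Day 21 gives 78.9%, while one missing KRYSTEXXA Day 14 gives 89.3%. The sample size does not change.
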